Somatostatin receptor scintigraphy using [¹¹¹In-DTPA-D-Phe]-pentetreotide (Octreoscan, OCT), an analog of somatostatin, may identify gastroenteropancreatic tumors, carcinoids, and medullary thyroid carcinomas, all of which express somatostatin receptors (12). The conventional 6 mCi dose of OCT has been reported to localize ectopic ACTH production, at NIH and elsewhere (12-14). De Herder et al. reported a sensitivity of 78% for Octreoscan in patients with ectopic ACTH production (15). However, at NIH, our experience with somatostatin receptor scintigraphy using the conventional dose of 6 mCi of [¹¹¹In-DTPA-D-Phe]-pentetreotide has not been as promising. Detectability of lesions in scintigraphic studies depends not only on the size of the lesion but also on the amount of radioactivity in that lesion. Thus, in the original version of this protocol, we investigated whether a higher dose of radiopharmaceutical could lead to higher concentrations in a lesion and better visualization. In thyroid cancer, it is known that higher doses of ¹³¹I can detect more lesions than lower doses. Furthermore, investigators using high doses of [¹¹¹In-DTPA-D-Phe]-pentetreotide for therapy (180 mCi) have seen more lesions on patients' post therapy scans as compared to their diagnostic scans (16). Analysis of 27 patients with surgically-proven ectopic ACTH-secreting tumors showed a 59% sensitivity for the "low dose" (6 mCi, L-OCT). In patients who had negative L-OCT, "high dose" (18 mCi, H-OCT) had an additional 58% (7/12 patients) sensitivity (17). As a result, the project was amended in 2006 to consider the high dose Octreoscan a medically-indicated test.

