Patients without active hypercortisolism in whom the standard Octreoscan is negative (or those ineligible for the mifepristone study) will undergo H-OCT. Because of interference we will wait at least one week after dosing a low dose Octreoscan before doing a H-OCT. The IRB previously agreed that this would be a medically indicated procedure in these patients. However, because it adds significantly to the cumulative radiation exposure, we have decided to limit this to three scans at intervals of at least one year.

The duration of standard imaging studies is about 10-15 minutes for either CT of the neck, chest, abdomen, or pelvis and 1-2 hours for either MRI of the pituitary, chest, abdomen, or pelvis, and 1-3 hours for Octreoscan (see below).

Research Procedures

Eligible patients with active hypercortisolism will receive the mifepristone-L-OCT combination as a research study (see below). Patients will undergo F-DOPA PET/CT as a research study, up to two studies with an interval of at least 12 months. Patients may undergo imaging before or after treatment of ectopic Cushing syndrome (if they have evidence of active ectopic ACTH secretion). Because of interference and to allow for administration of mifepristone, we will wait at least ten days after dosing a low dose Octreoscan before doing a second L-OCT. A gated chest MRI will be obtained using a 3 Tesla magnet with T1 and T2 sequences. Blood will be collected into one heparin and serum tube and an aliquot of urine will be retained for additional clinical or future research studies related to hypercortisolism. As an example, we previously studied the utility of pro-calcitonin using research samples collected under another protocol (39). Patients will be asked to consent to the future use of tumor samples. If they consent to such use, samples may be used in the future, with identifiers, for studies not described here, without obtaining new informed consent. Only studies related to Cushing's syndrome or the biology of tumors would be undertaken.

F-DOPA PET/CT procedures

The research team is responsible for ensuring that PET-specific regulations and procedures are followed.

Patients are studied in the PET Department scanning facility at the Clinical Center after a minimum of 6 hours fasting. A plastic catheter is inserted into an arm vein. Patients receive carbidopa, 200 mg, orally 60 minutes before the scheduled injection of F-DOPA.

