The IRB previously approved an accrual ceiling of 202 for the high dose octreoscan component. That component is no longer a part of the protocol. Eighty-nine patients have enrolled in the protocol. F-DOPA PET was positive in 8 of 17 patients with known tumors and high dose Octreoscan was positive in 7 of 12.

Given these encouraging results, we propose performing F-DOPA in a total of at least 30 patients. The current results imply an estimated success rate of about 55% for each modality; the plausible range for the true success rate ranges from about 26 to 80% using a 95% confidence interval, a very broad range.

Studying a total of 30 patients will allow us the possibility of precluding a true success rate of under 20% (with 95% confidence) if we were to see no additional successes. If there are additional successes in the additional patients the confidence interval for what the true probability of success could be will still be fairly broad. Since limited patients have been evaluated using F-DOPA, we ask that the overall accrual ceiling remain intact and that it be altered based on annual reports of the results. Additionally, we have essentially no data on which to base a sample size calculation for the mifepristone study, and would recalculate accrual limits when such data are available.

Data Collection and Evaluation

Staff in the Departments of Radiology will evaluate the conventional studies. [name] reviews the F-DOPA PET/CT without knowledge of the results of other localization studies. [name] reviews all studies. Data are maintained by the NICHD Clinical Trials DataBase.

The study will be analyzed in collaboration with [name] (Clinical Center Statistics Center). Data are collected and analyzed with regard to the sensitivity, specificity, accuracy, and predictive value for each scan being evaluated. The exploration and pathologic analysis is used as the reference standard. McNemar's test for evaluating paired data will be used (40). In addition to McNemar's test, other approaches to evaluation of the four objectives are below:

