(a) *Compared to other imaging techniques, is the sensitivity and specificity of F-DOPA PET/CT higher in detecting the source of ectopic ACTH production in patients with known and unknown tumor localization?* To determine this, we will calculate the sensitivity, specificity, positive and negative values in patients with proven tumors and compare these with the results from the other modalities. Confidence intervals will be calculated and overlapping results will indicate that the modalities are similar. We cannot perform these calculations for unknown tumors, but can compare the overall percentage of tumors found of all imaged using each technique.

(b) *Does a correlation exist between F-DOPA uptake and the type of tumor, its size and proliferative activity?* To do this, we will evaluate the percent of each type of tumor that has a positive F-DOPA scan. Confidence intervals will be used to compare across tumor types. Univariate logistic regression will be performed using size and mitotic index as the variables.

(c) *Can the administration of mifepristone, 600 mg daily for 10 days, convert a negative standard 6 mCi OCT (L-OCT) to a subsequent positive result?* This will be a descriptive analysis, indicating the percentage of tumors that convert the test to a positive result. A post-hoc analysis will compare this percentage to the historical percentage of tumors that are positive on high but not low dose octreoscan.

(d) *Does gated chest MRI detect more lesions than routine MRI?* A similar approach will be used, to look at the percentage of known tumors that are detected by gated vs routine MRI and comparing confidence intervals around those values.

PHARMACEUTICAL AND RADIATION SAFETY

Pharmaceutical Information: F-DOPA

F-DOPA is a radiolabeled amino acid (^{18}F has a 109 minute half-time). It is approved by the FDA for use under IND # 35513. [name], Chief, PET Department, holds the IND. F-DOPA is produced as outlined in the IND. F-DOPA has been used in many protocols at the NIH and at other centers throughout the world. The formulation is prepared on the day of use and assayed in a dose calibrator. The total amount of F-DOPA will typically be ~2.4 mg and will not exceed 6.5 mg.

Pharmaceutical Information: [^{111}In -DTPA-D-Phe]-pentetreotide

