3. Consent for (previous or new) patients who are hypercortisolemic and refuse or are not candidates for mifepristone, or those who are not hypercortisolemic. On each admission they will get standard imaging (CT, MRI, 6 mCi OCT) as well as F-DOPA PET and high dose octreoscan (if low dose is negative), up to the maximum number of PET and high dose octreoscans.

We do not plan or anticipate the enrollment of non-English speaking subjects; however they are not excluded from participation either. Should a non-English speaking subject be eligible for enrollment, IRB approval will be obtained for use of the short form consent process in the absence of a fully translated consent document as outlined in SOP 12.9.1, under the provisions of 45 CFR 46.117(b)(2). IRB approval will be obtained according to IRB guidance prior to obtaining informed consent from the potential study participant/s.

Employee enrollment is not anticipated in this protocol, but if an employee wants to be enrolled in the study with the prospect of direct benefit in accordance with the policy SOP 14F.3.1 the PI is not required to amend the protocol. However the PI will take the following steps to ensure that there are adequate protections in place to protect the confidentiality of employee health information and minimize any pressure or discomfort of the employee with consent process.

1. The PI or responsible AI will make the NIH Information Sheet on Employee Research Participation available to employees who are considering enrolling in research to help them understand the possible consequences. Also, the PI or AI will make a copy of the NIH policy 2300-630-3 available to employee.
2. If PI or AI is the supervisor of the employee-subject an independent person (i.e. bioethics staff) will monitor consent process.
3. The PI will require that study staff who may have contact with sensitive data about a co-worker or subordinate complete the Just-in-Time CITI course "Biomedical –Vulnerable Subjects-Workers/Employees".

Confidentiality and use of retained tissue specimens

Confidentiality of patients is assured according to the laws of the State of Maryland. When results of a study such as this are reported at meetings or in medical journals, the identification of those patients taking part is withheld. Medical records of Clinical Center patients are maintained according to current local requirements and are made available for review, as required by the FDA or other authorized users.

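### One success rate of about 55% (26 to 80%) is given for F-DOPA PET and high-dose Octreoscan, but the counts give 47% and 58% in differently selected patients, and the unpaired comparisons in objective (a) could repeat the mismatch

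*Combined protocol and SAP*

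**What the plan says.** Under Justification of the number of subjects, the protocol reports: "F-DOPA PET was positive in 8 of 17 patients with known tumors and high dose Octreoscan was positive in 7 of 12". It continues: "The current results imply an estimated success rate of about 55% for each modality". One range is given for the true rate, which "ranges from about 26 to 80% using a 95% confidence interval". These figures lead into the proposal to perform F-DOPA PET in at least 30 patients.

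The Introduction shows where the 7 of 12 comes from. "Analysis of 27 patients with surgically-proven ectopic ACTH-secreting tumors showed a 59% sensitivity for the" 6 mCi scan (L-OCT). Among patients with a negative L-OCT, the 18 mCi scan (H-OCT) "had an additional 58% (7/12 patients) sensitivity". The same selection continues under Standard Medical Evaluation of Cushing Syndrome: "Patients without active hypercortisolism in whom the standard Octreoscan is negative (or those ineligible for the mifepristone study) will undergo H-OCT". Consent form 3 carries the same condition. Neither Research Procedures nor the consent section makes F-DOPA PET depend on the L-OCT result.

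Data Collection and Evaluation plans McNemar's test for paired data and then adds further methods for each objective. For objective (a), sensitivity, specificity and predictive values are calculated in proven tumors, and overlapping confidence intervals are read as showing that modalities are similar. For unknown tumors the plan is to "compare the overall percentage of tumors found of all imaged using each technique".

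**The concern.** A reader of the sample-size section would conclude that F-DOPA PET and H-OCT have been observed to perform equally, at about 55%. The counts do not say that. The H-OCT figure was obtained only in patients in whom the low-dose scan had already failed. No such restriction is stated for the F-DOPA figure.

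The same mismatch could enter the analysis. If H-OCT is among the techniques compared with F-DOPA in objective (a), a percentage with a separate denominator for each technique sets an L-OCT-negative subset against patients not selected by L-OCT. The interval-overlap rule has the same weakness. The resulting difference, or apparent similarity, would mix scanner performance with patient selection.

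**Working it through.** **Inputs.** F-DOPA 8/17 and H-OCT 7/12 (Justification of the number of subjects). H-OCT 7/12 conditional on a negative L-OCT, and L-OCT sensitivity 59% in 27 proven tumors (Introduction). An earlier F-DOPA result of 6/11 (Introduction). Stated rate about 55%, stated interval about 26 to 80%.

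**1. Can the 55% be reproduced?**
- F-DOPA: 8/17 = 47.1%
- H-OCT: 7/12 = 58.3%
- Pooled: (8 + 7)/(17 + 12) = 15/29 = 51.7%
- Simple average: (47.1 + 58.3)/2 = 52.7%
- Earlier F-DOPA count: 6/11 = 54.5%

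Nothing built from the two counts in that section comes within 2 points of 55%. The earlier 6/11 does.

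**2. Can the 26 to 80% be reproduced?** 95% intervals:
- 8/17: exact (Clopper-Pearson) 23.0 to 72.2%; Wilson 26.2 to 69.0%
- 7/12: exact 27.7 to 84.8%; Wilson 32.0 to 80.7%
- 15/29: exact 32.5 to 70.6%
- 6/11: Jeffreys 27.0 to 80.0%; exact 23.4 to 83.3%

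No interval for 8/17, 7/12 or their pool matches. Two constructions come within about a point: the Jeffreys interval for the earlier 6/11, and the Wilson lower limit for F-DOPA (26.2) joined to the Wilson upper limit for H-OCT (80.7). The first would mean the sentence was not updated when the count became 8/17. The second would mean that two patient sets were merged into one interval. Either origin is an inference, since the documents do not give the method.

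**3. Are the two rates for the same kind of patient?** By the Introduction, the 12 H-OCT patients were all L-OCT negative. The 17 F-DOPA patients are described only as having known tumors, and their split by L-OCT result is not given. F-DOPA's rate among L-OCT negatives, which would be the matched figure, cannot be computed.

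**4. What would the unpaired rules do with these counts?** The exact intervals, 23 to 72% and 28 to 85%, overlap. Objective (a) would then call the modalities similar, although one was tested only where L-OCT had failed.

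**5. How far could conditioning matter?** On a base of all proven tumors, L-OCT followed by H-OCT in the negatives would find

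p(L+) + (1 − p(L+)) × p(H+ | L−) = 0.59 + 0.41 × 7/12 = 0.83.

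Putting in only the exact limits for H-OCT gives 0.59 + 0.41 × 0.277 = 0.70 to 0.59 + 0.41 × 0.848 = 0.94. The inputs do not fit together exactly: 59% of 27 is about 16, which leaves 11 L-OCT negatives, yet H-OCT is reported in 12. The 83% is indicative only.

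**The case against.** The sample-size sentence describes how imprecise the current data are. It does not test F-DOPA against H-OCT, and no number is derived from such a comparison. This stands: the target of at least 30 does not change because of this point. (Whether 30 patients deliver the precision that the section goes on to claim is a separate question.)

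McNemar's test is planned, and for F-DOPA against H-OCT it can use only patients who had both scans, essentially L-OCT negatives. This largely stands, so the plan as a whole cannot be called unpaired. What remains is that the additional methods for objective (a) are unpaired, and that a McNemar result involving H-OCT would itself need labelling as conditional on a negative L-OCT.

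H-OCT may not be a comparator at all. Objective (a) names no techniques, and the protocol says the H-OCT component has ended. This stands in part. H-OCT continues as a clinical scan that produces results, and nothing excludes it. CT, MRI and L-OCT are standard for all these patients, so the selection problem does not touch them.

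The percentage of all imaged is only the fallback for unknown tumors. That is correct, and the 83% figure, which comes from proven tumors, does not measure its effect there.

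A reader might also infer that F-DOPA is about 36 points worse than the low-then-high sequence (83% less 47%). The documents do not support that. The figure sets two scans against one, in small and unmatched samples whose counts do not agree. The ranges of 70 to 94% and 23 to 72% overlap slightly, and the first ignores the uncertainty in the 59%. The F-DOPA technique has also changed, with carbidopa added in 2008 and PET/CT now introduced.

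**Conclusion.** The concern holds in a limited form. The common rate of about 55% and the common interval of 26 to 80% do not follow from the section's own counts. The correct figures are 47% (23 to 72%) for F-DOPA in patients with known tumors, and 58% (28 to 85%) for H-OCT in L-OCT-negative patients. For F-DOPA the stated rate is about 8 points too high, and the stated upper limit is about 8 points above the exact one.

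The consequence for objective (a) depends on an assumption the text leaves open, namely that H-OCT is one of the comparators. If it is, the unpaired percentages and the interval-overlap rule compare an L-OCT-negative subset with patients not selected by L-OCT.

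The documents do not show that F-DOPA was scored in all patients (the 17 had known tumors), that the sample size is invalid, or that a 36-point deficit has been measured.

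**What to change.** - In Justification of the number of subjects, replace the common rate and interval with 47% (exact 95% interval 23 to 72%) for F-DOPA in patients with known tumors and 58% (28 to 85%) for H-OCT in L-OCT-negative patients. Name the interval method.
- In objective (a), list the comparator techniques and say whether H-OCT is one of them.
- Make every F-DOPA comparison in patients who had both scans, shown as a paired two-by-two table with McNemar's test.
- If H-OCT is included, either label its result as conditional on a negative L-OCT, or compare F-DOPA with the L-OCT-then-H-OCT sequence. For the sequence, report how many L-OCT-negative patients had no H-OCT, for example because they entered the mifepristone study. Dropping them silently would over-represent L-OCT positives.
- For H-OCT, do not use the unpaired percentage of all imaged or the interval-overlap rule.

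This costs wording and one extra table. The drawback is that the H-OCT comparison will rest on fewer patients and be less precise.

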We found that F-DOPA PET substantiated a lesion seen on CT and/or MRI scan in 6 of 11 patients, including some with questionable results on conventional imaging. We amended the protocol in 2008 to administer carbidopa, 200 mg, one hour before the study. [name] has found that this strategy improves tumor detection of pheochromocytoma, presumably by inhibiting decarboxylation of the tracer. This amendment will now allow us to perform FDOPA PET/CT, which was not available previously.

The project was amended in 2004 regarding the routine chest MRI scans. We initially obtained images on a 0.5 T magnet using, using STIR, T1 and T2 images. Subsequently a 1.5 T magnet replaced the lower strength magnet and STIR images were not obtained. Recently a 3.0 T magnet has become available with image acquisition gated to the EKG R-R interval so that artifact from cardiac motion is reduced. Our collaborator [name] has performed T1 and T2 sequences using this approach with excellent resolution of mediastinal and chest structures. Increased strength of magnetic field compared to conventional 1.5T MRI allows for a stronger signal and therefore improved signal to noise ratio. Free breathing techniques are used to avoid breath holding, which may be difficult for those patients with volume overload. The combination of higher signal and decreased motion artifacts should significantly improve resolution allowing for better delineation of small lesions that may be responsible for ectopic ACTH production. To test this, we have added these sequences.

We wish to clarify the use of chest CT scans, as the available modalities have changed. A “surgical chest protocol CT” (which involves thin (1-2mm) cuts throughout the thorax) will be obtained at each visit.

For the initial imaging, gated “cardiac CT” will be obtained as well to look for retrocardiac lesions that can be obscured by non-gated routine CT. However, because of the amount of radiation, we will obtain this scan only at the initial visit, unless there is a subsequent clinical suspicion of a retrocardiac lesion.

OBJECTIVES

Specific questions to be addressed:

F-DOPA PET/CT

(a) Compared to other imaging techniques, is the sensitivity and specificity of F-DOPA PET/CT higher in detecting the source of ectopic ACTH production in patients with known and unknown tumor localization?

(b) Does a correlation exist between F-DOPA uptake and the type of tumor, its size and proliferative activity?

Octreoscan

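### With no further positives, 30 F-DOPA patients exclude only true rates below about 12–14%, not 20%; and the 55% rate quoted for each modality does not match the current 8/17

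*Combined protocol and SAP*

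**What the plan says.** Under *Analysis of the Study – Justification of the number of subjects*, the combined protocol and SAP reports the results to date: "F-DOPA PET was positive in 8 of 17 patients with known tumors and high dose Octreoscan was positive in 7 of 12". On that basis it says "we propose performing F-DOPA in a total of at least 30 patients".

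It then summarises the data: "The current results imply an estimated success rate of about 55% for each modality", with a 95% range of about 26% to 80%. Neither the interval method nor its sidedness is given.

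The one inferential property claimed for 30 patients is that they offer the possibility of "precluding a true success rate of under 20% (with 95% confidence) if we were to see no additional successes". The text adds that, if there are further successes, the interval will still be fairly wide.

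The Introduction gives another F-DOPA count: "We found that F-DOPA PET substantiated a lesion seen on CT and/or MRI scan in 6 of 11 patients".

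**The concern.** Adding 13 negative scans to 8/17 brings the observed rate down to 26.7%. With only 30 patients, a lower confidence limit of 20% would then lie less than 7 percentage points below the estimate, which is implausibly tight.

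The quoted rate also looks wrong. Neither current count is 55%, and F-DOPA, the modality being sized, is clearly below it. The figure does match 6/11 in the Introduction.

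At stake is the only quantitative argument for giving research F-DOPA scans to at least 13 more patients. The sentence describes the unfavourable case, in which every new scan is negative. A reader of the annual results, on which the accrual ceiling is to be revisited, would wrongly believe that a rate under 20% had been excluded.

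**Working it through.** **Inputs.** F-DOPA 8/17, high-dose Octreoscan 7/12 and a planned total of 30 come from *Justification of the number of subjects*. F-DOPA 6/11 comes from the Introduction. The additional patients number 30 − 17 = 13. All 13 are taken as evaluable on the same basis as the first 17, that is, as patients with known tumors.

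**1. The claimed property.** No additional successes gives 8 + 0 = 8 positives in 30, and 8/30 = 26.7%. The exact (Clopper–Pearson) lower limit is the rate p that solves P(X ≥ 8 | n = 30, p) = α, with α = 0.025 for two-sided and 0.05 for one-sided 95% limits. The plan names no method, so the common ones are all shown.

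| Method | Two-sided 95% lower limit | One-sided 95% lower limit |
|---|---|---|
| Exact | 12.3% | 14.0% |
| Wilson | 14.2% | 15.7% |
| Agresti–Coull | 14.0% | 15.6% |
| Jeffreys | 13.5% | 15.3% |
| Wald | 10.8% | 13.4% |

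The limits run from 10.8% to 15.7%, and none reaches 20%. As a direct check, P(X ≥ 8 | n = 30, p = 0.20) = 0.239. If the true rate were 20%, a result at least this good would occur about one time in four. The plan's figure is not reproduced.

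**2. Other starting counts.** Starting from 6/11 gives 6/30 = 20.0%, exact two-sided 95% interval 7.7% to 38.6%. Starting from 7/12 gives 7/30 = 23.3%, interval 9.9% to 42.3%. Both are further from the claim. In the first case 20% is the point estimate itself.

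**3. How far 8 positives can stretch.** The exact lower limit for 8 successes stays above 20% only while the total is no more than 19 (two-sided: 8/19 gives 20.3%, 8/20 gives 19.1%) or 21 (one-sided: 8/21 gives 20.6%, 8/22 gives 19.6%).

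**4. What 30 patients need.**

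| Positives of 30 | Of the next 13 | Exact two-sided lower limit | Exact one-sided lower limit |
|---|---|---|---|
| 8 | 0 | 12.3% | 14.0% |
| 10 | 2 | 17.3% | 19.3% |
| 11 | 3 | 19.9% | 22.1% |
| 12 | 4 | 22.7% | 25.0% |

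Excluding 20% therefore needs 12/30 by exact two-sided limits and 11/30 by exact one-sided limits. Wilson limits need 11/30 two-sided (21.9%) or 10/30 one-sided (21.1%). If the true rate is 8/17 = 47%, the chance of at least 4 positives in 13 is 0.93, and of at least 3 it is 0.98.

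**5. The quoted rate and range.**

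| Count | Rate | Exact 95% | Wilson 95% |
|---|---|---|---|
| F-DOPA 8/17 | 47.1% | 23.0–72.2% | 26.2–69.0% |
| High-dose Octreoscan 7/12 | 58.3% | 27.7–84.8% | 32.0–80.7% |
| Both pooled 15/29 | 51.7% | 32.5–70.5% | 34.4–68.6% |
| F-DOPA 6/11 (Introduction) | 54.5% | 23.4–83.3% | 28.0–78.7% |

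Only 6/11 rounds to 55%. Against 8/17 the stated rate is 55 − 47 = 8 percentage points too high. The printed 26–80% is not the exact interval of either modality, and no standard interval for 8/17 has an upper limit near 80%.

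**The case against.** The strongest defences fall into three groups.

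**Other readings of the 20% sentence.** It speaks of a possibility, not a guarantee. But its condition of no further successes leaves one outcome, and that outcome fails.

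The current count covers patients with known tumors, whereas 30 is the number to be scanned, so the evaluable denominator could be smaller. The sentence would hold by exact limits if that denominator were no more than 19 (two-sided) or 21 (one-sided), meaning that only 2 to 4 of the 13 new patients had known tumors. The text does not say this. The point does stand as a reason to state the denominator.

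Finally, 0 of 13 has a one-sided exact upper limit of 20.6%. That bounds the rate from above, the opposite of what is written, and ignores the 8 successes.

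**The 55% and the 26–80% range.** No calculation uses the 55%, 30 is not derived from it, and it lies inside the interval for 8/17. The range could be a blend, with 26.2% as the Wilson lower limit for 8/17 and 80.7% as the Wilson upper limit for 7/12. That is fair: the range may come from current data. The 6/11 count is also worded differently, as lesions already seen on CT or MRI, so carry-over from it is a plausible inference and no more. Even so, 55% is not the rate for each modality, and a blended range is not an interval for F-DOPA.

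**Consequences.** No stopping rule or test uses 20%, the plan admits wide intervals, and its analysis section would report an honest interval at 8/30. This limits the harm to the justification itself, but does not make the justification true.

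**Conclusion.** The concern holds. With 8 positives in 30, the data exclude only true rates below about 12% (exact two-sided) or 14% (exact one-sided). The claim of 20% fails under every standard method, with lower limits between 10.8% and 15.7%. Excluding 20% at 30 patients takes 3 or 4 positives among the next 13 by exact limits, not none.

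The stated 55% is about 8 percentage points above the current F-DOPA rate of 47%. This second error does not change the sample size.

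The result assumes that all 30 patients count in the denominator and that 8/17 is the starting point; starting from 6/11 or 7/12 makes the shortfall larger. It does not show that 30 is too few, and the planned analyses are unaffected. Because this sentence is the only inferential support for the number, it must be corrected.

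**What to change.** Keep the total at 30 and replace the rate, the range and the 20% sentence with text along these lines:

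> To date F-DOPA PET is positive in 8/17 (47%; exact 95% CI 23–72%) and high-dose Octreoscan in 7/12 (58%; 28–85%). Among 30 patients with known tumors, if no further positives are seen, 8/30 (27%) has an exact two-sided 95% CI of 12–46% and does not exclude 20%. A true rate below 20% is excluded if at least 12 of 30 are positive, that is, at least 4 of the next 13. With 14 to 16 positives the 95% CI would run from 28–66% to 34–72%.

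The text should name the interval method and its sidedness, and say that the denominator is patients with known tumors. If 30 is instead the number scanned, the expected number with known tumors should be given and the limits recalculated.

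The cost is a few sentences. No patient, procedure or analysis is added. The stated property becomes less favourable, but the 20% goal stays within reach: the chance of at least 4 positives in 13 is 93% if the true rate is 47%.
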